- Participant Recruitment and Informed Consent: All study recruitment and C.8.2. consent activities will be conducted onsite at the TMC. Using the NCI screening log, the research coordinator will systematically screen all TMC patients who require palliative care for study eligibility. Inclusion criteria: age 18+, any cancer type of which the PI feels have a cluster of symptoms that can be managed at home and not require hospitalization, late stage cancer, an ECOG status of 0-3, residence in 24 Parganas regions, physician documentation in paper medical record that patient is to receive palliative care, and patient willingness to participate in data collection. These broad eligibility criteria will be used, as the study will evaluate the intervention under real world conditions. For patients who meet eligibility criteria, the research coordinator will introduce the study and assess interest in participation. Interested patients will be referred to their palliative oncologist to answer questions about the study and complete informed consent. Next, the palliative care physician will randomly assign patients to intervention or control group. For each patient screened, the research coordinator will document if patient was offered, consented to and dropped out of study, and reasons for screen failure and drop out. This will enable assessment of feasibility of our recruitment plan, plus generalizability of study participants to the 24 Parganas Regions. Participants will receive \$15 for study participation upon study enrollment and at each of three follow-up survey intervals towards their travel expenses.

Table 2: Evaluation Measures Organized within the REAIM Framework			
Outcome	Measures	Collection/Time Points	
Aim 1: Evaluation of Intervention Implementation			
CHW Training/ Orientation	Attendance rates for program orientation, trainings and meetings among CHWs and clinical team; Pre/post-test change in CHW's palliative care knowledge and perceptions; CHW's skills performance and perceptions of training content and format post-training	Minutes from home-based palliative program meetings TMC Co-ls will administer	
		survey pre-post training & skills checklist post-training	
CHW Role	Frequency of patient visits; assessment of patient problems (e.g. pain, transportation, depression); CHW actions (education, scheduling appt., obtaining morphine); problem resolution (pain control); frequency of debriefings with clinicians	Review of toolkit log data	

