- C.9.1. Patient Surveys. Surveys will be conducted with study participants at study entry (baseline) and at 1, 3 and 6 months to assess patient outcomes. The TMC research coordinator, a native Bengali speaker, will administer the baseline survey after informed consent and will travel to patient homes to administer follow up surveys. As patients have low literacy and are very sick, we selected brief instruments that use simple language and response options. Multi-dimensional palliative care outcomes will be assessed with the 10-item African Palliative Outcomes Scale that measures physical and psychological symptoms; spiritual, practical and emotional concerns; and psychosocial needs of patient/family on a 5-point likert scale.²⁴ QOL will be assessed with the 26-item WHO QOL Scale, 25-27 that assesses physical health, psychological health, social relationships and environment on a 5-point likert scale. Cancer symptoms will be assessed with the 9-item Edmondton Symptom Scale. 29-30 Experience with care will be assessed with the 16-item FamCare Patient Scale³⁰⁻³¹ measured on a 5-point likert scale. These instruments have established validity and reliability and have been used in palliative populations and limited resource settings including India, but have not been translated into Bengali. Surveys will be translated using standard translation/back translation to ensure accurate translation.
- C.9.2. Palliative Care Toolkit Forms. Toolkit forms^{3,33} include: 1) a record of patients in CHW's caseload; 2) a home visit record to track services, including main problems, care provided and visit notes; 3) a patient-held home care record to longitudinally document visits to patient, their condition and main problems, care provided and notes;

- 4) a patient-held drug chart to record name and purpose of each drug, dose and form of medication, and when each dose should be taken; 5) a patient held morphine record to document form, strength, and administration dates/times; 6) a referral form for services and resources; and 7) a monthly report to document number of patients under care, their diagnoses and contacts, new referrals, and end of care outcomes.

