- C.9.3. Post-Intervention Interviews. [name], who is a well-trained interviewer and speaks Bengali, will interview stakeholders to evaluate the intervention. She will conduct 20 in-person interviews (or until saturation is reached), representing all Pal-Care clinical team members (n=6) and CHWs (n=6) and 8 patients/caregivers who participated in the intervention. Patients/ caregivers will be purposefully selected to represent experiences across different cancers, clinical problems and assigned CHWs. To fill in information gaps, additional stakeholders may be interviewed. Qualitative recommendations suggest thematic saturation is usually achieved with 15-30 participants. 11 We will obtain informed written consent and provide \$10 participant compensation. Clinical team and CHW interviews will guery how CHW's conducted their work, training and support needed, and barriers, facilitators and optimal strategies for delivering care. Patient/caregiver interviews, to be conducted in patient homes, will query experiences with the CHW, education and support needed and if these needs were met, and service quality and efficiency (§Appendix). Interviews will be digitally recorded, transcribed and analyzed in N-Vivo software. 34 The data collection protocol will take <1 hour.
- **C.11. Sample Size.** For this pilot study, we will recruit 45 patients in the intervention and control groups (n= 90). As advocated by Leon, pilot studies "serve to check availability of eligible and willing subjects using the recruitment methods proposed, test feasibility of the treatment and measurement protocols, train researchers in study tasks, and set up data collection, checking, storage, and retrieval capabilities." Leon also noted that pilots are deficient in estimating effect size with sufficient accuracy for future study design. Thus, we will monitor the multiple process measures indicated in **Table 2** and obtain estimated variability of primary outcome measures. For a total sample of 90 participants, 95% CI estimates of *between groups* difference in change scores of palliative needs, pain, QOL and cancer symptom burden for the 2 groups can be estimated with precision ranging from ±1.0 to ±2.1 for standard deviations of difference scores ranging from 2.5-5.0 SD units.

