- **C.12. Analysis Plan:** Table 2 describes measures to be collected to evaluate study aims. Data will be analyzed in SAS.³⁶ For aim 1, implementation mesures will be reported as means, standard deviations, medians, range, frequencies and proportions as appropriate. When appropriate, outcomes will be compared between intervention and control groups using t-tests and chi-square tests (or equivalent nonparametric tests) as appropriate. For primary analyses for aim 2 the intent-to-treat (ITT) sample will be used comprising all randomized patients. Descriptive statistics will be calculated for all variables. For continuous variables we will report means, standard deviation, medians and ranges. We will compare between group differences for continuous variables using either t-test for variables that are normally distributed or can be log-transformed or a Wilcoxon rank sum test for variables if normality cannot be approximated. For categorical variables, we will report frequencies, percentages and compare between group values with Chi Square or Fisher exact test. 95% CIs will be

reported. In exploratory analysis to obtain variance estimates of effectiveness outcomes and the covariance structure of the longitudinal scores, generalized linear mixed models (GLMM) will be used to compare the two groups (intervention vs. control group) with intervention group as the primary independent variable and pain as the dependent variable. GLMM can account for clustering of measurements within CHW and within patients as well as accommodate missing data. Group (intervention vs. control group) will be a fixed effect; demographics (age, gender, distance from cancer center); and clinical (time since diagnosis, cancer type, baseline pain) variables will be adjusted for, along with a CHW variable accounting for cluster effects among patients by CHW. We will estimate the difference (via 95% CI) in average slopes between intervention and control groups and evaluate linearity of trajectories as input to inform a future trial. Further, dropout rate will be examined. If over 10% of data are missing, we will adjust data collection intervals in a future trial.

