Analysis Plan: Outcome measures as described in Results were collected to evaluate study aims. Data will be analyzed in SAS. All measures will be evaluated overall and by patient age, gender and cancer type and by CHW caseload. For aim 1, implementation mesures will be reported as means, standard deviations, medians, range, frequencies and proportions as appropriate. When appropriate, outcomes will be compared between intervention and control groups using t-tests and chi-square tests (or equivalent nonparametric tests) as appropriate. For primary analyses for aim 2 the intent-to-treat (ITT) sample will be used comprising all randomized patients. Descriptive statistics will be calculated for all variables. For continuous variables we will report means, standard deviation, medians and ranges. We will compare between group differences for continuous variables using either t-test for variables that are normally distributed or can be log-transformed or a Wilcoxon rank sum test for variables if normality cannot be approximated. For categorical variables, we will report frequencies, percentages and compare between group values with Chi Square or Fisher exact test. 95% CIs will be reported. In exploratory analysis to obtain variance estimates of effectiveness outcomes and the covariance structure of the longitudinal scores, generalized linear mixed models (GLMM) will be used to compare the two groups (intervention vs. control group) with intervention group as the primary independent variable and pain as the dependent variable. GLMM can account for clustering of measurements within CHW and within patients as well as accommodate missing data. Group (intervention vs. control group) will be a fixed effect; demographics (age, sex, distance from TMC cancer center); and clinical (time since diagnosis, cancer type, baseline pain) variables will be adjusted for, along with a CHW variable accounting for cluster effects among patients by CHW. We will estimate the difference (via 95% CI) in average slopes between intervention and control groups and evaluate linearity of trajectories as input to inform a future trial. Further, dropout rate will be examined. If over 10% of data are missing, we will adjust data collection intervals in a future trial.

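### The Aim 2 primary comparisons are labelled intention-to-treat, but with no rule for deaths they default to comparisons among survivors, and the 10% missing-data rule mixes deaths with missed surveys

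*Protocol*

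**What the plan says.** Eligibility (protocol C.8.2) includes "late stage cancer, an ECOG status of 0-3" and documentation that the patient is to receive palliative care. On follow-up, C.9.1 states: "Surveys will be conducted with study participants at study entry (baseline) and at 1, 3 and 6 months to assess patient outcomes". Table 2 lists surveys only after baseline and at 1 and 3 months, so the two places must be reconciled.

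For the Aim 2 primary analyses the SAP says "the intent-to-treat (ITT) sample will be used comprising all randomized patients", and protocol C.12 says the same. Continuous outcomes are compared by t-test or, where normality fails, by Wilcoxon rank sum test. Neither document says what value, rank or status a patient without a score receives.

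Three provisions touch on incomplete data, and they are the same in both documents:

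- Of the mixed model, "GLMM can account for clustering of measurements within CHW and within patients as well as accommodate missing data". That model is exploratory and has pain as its only dependent variable.
- The dropout rate will be examined.
- "If over 10% of data are missing, we will adjust data collection intervals in a future trial".

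Death appears in neither analysis plan. It does appear in Table 2, where survival days and location of death come from the health workers' toolkit forms for the intervention group.

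On precision, C.11 and the SAP say "we will recruit 45 patients in the intervention and control groups", with "precision ranging from ±1.0 to ±2.1 for standard deviations of difference scores ranging from 2.5-5.0 SD units".

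**The concern.** Deaths before the later surveys are foreseeable in this population. A t-test or rank test on survey scores can use only patients who have a score. Someone following the plan literally would drop the dead and still report the result as covering everyone randomized. Survivors are not a randomized subset: if one arm keeps sicker patients alive longer, its survivors can score worse for that reason alone.

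Two further consequences need no survival difference between arms. First, the 10% rule is the only missing-data threshold in the plan. If deaths count towards it, crossing it says little about survey burden. Second, the precision statement makes no allowance for patients who never supply a change score. Both matter because the pilot's declared products are variability, slopes and dropout for designing a larger trial.

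**Working it through.** **Inputs from the documents:** 45 per arm, 95% CI, SD of change 2.5 to 5.0 (C.11); surveys at 1, 3 and 6 months (C.9.1).

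**Assumed, because the documents give no figure:** mortality by arm, the correlation ρ between score and liability to die, and the timing of deaths.

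**1. The plan's own precision.** Half-width = 1.96 × SD × √(2/45).

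- SD 2.5: 1.96 × 2.5 × 0.2108 = 1.03
- SD 5.0: 1.96 × 5.0 × 0.2108 = 2.07

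With t on 88 df these become 1.05 and 2.09. Either way the stated ±1.0 to ±2.1 is reproduced, using all 45 per arm.

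**2. Precision with deaths, equal in both arms (assumed).** Replace 45 by 45 × (1 − d).

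| Deaths d | Left per arm | SD 2.5 | SD 5.0 |
|---|---|---|---|
| 0% | 45 | ±1.03 | ±2.07 |
| 20% | 36 | ±1.15 | ±2.31 |
| 30% | 31.5 | ±1.23 | ±2.47 |
| 40% | 27 | ±1.33 | ±2.67 |
| 50% | 22.5 | ±1.46 | ±2.92 |

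**3. Survivor-only shift with no true effect on scores.** Take a normal score correlated ρ with the severity that decides death. With mortality p, the survivor mean is displaced from the all-randomized mean by ρ × φ(z_p)/(1 − p) SD, in the healthier direction.

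- φ(z_p)/(1 − p): 0.497 at p = 0.30; 0.644 at p = 0.40; 0.798 at p = 0.50.
- 50% control vs 30% intervention: ρ × (0.798 − 0.497) = ρ × 0.301. This is 0.09, 0.15 and 0.21 SD for ρ = 0.3, 0.5 and 0.7.
- 40% vs 30%: ρ × 0.147. This is 0.04, 0.07 and 0.10 SD.
- Equal mortality with equal selection: 0.

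The shift runs against the arm with longer survival. For scale, the half-widths in SD units are:

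- 50% vs 30%: 1.96 × √(1/22.5 + 1/31.5) = 0.54
- 40% vs 30%: 1.96 × √(1/27 + 1/31.5) = 0.51
- no deaths: 1.96 × √(2/45) = 0.41

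The shift is therefore between 0.04/0.51 ≈ 8% and 0.21/0.54 ≈ 39% of the half-width.

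**4. Cross-check by simulation.** Death was made to depend on each patient's own symptom level and slope, with no effect of arm on scores and SD of change 3.2. With a hazard ratio for death of 0.6 (6-month deaths 42% vs 29%), mean change among survivors was 0.98 in control and 1.25 in intervention, against a true 1.80 in both. The spurious gap is 0.27 points, or 0.27/3.2 = 0.08 SD. At hazard ratios of 0.8 and 0.4 it was 0.13 and 0.42 points.

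**5. The mixed model.** On simulated data with 4,000 per arm, the between-arm slope difference was 0.025 per month both with equal hazards (SE 0.014) and with a hazard ratio of 0.6 (SE 0.013). No clear between-arm bias was shown. The control slope in the second run was 0.20 against a true 0.30.

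**6. The 10% rule.** Assume a constant hazard, 6-month mortality m, and no living patient missing a survey. The share dead at month t is 1 − (1 − m)^(t/6).

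| m | Month 1 | Month 3 | Month 6 | Mean of 3 follow-ups | Baseline also counted | Months 1 and 3 only |
|---|---|---|---|---|---|---|
| 20% | 3.6% | 10.6% | 20% | 11.4% | 8.6% | 7.1% |
| 30% | 5.8% | 16.3% | 30% | 17.4% | 13.0% | 11.1% |

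Deaths alone can cross the threshold. Whether they do depends on mortality, on the denominator and on which survey schedule applies.

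**The case against.** The plan is silent on death; it does not instruct anyone to treat death as missing. That is right. The survivor-only comparison is what the named tests produce when no rule is given.

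A reader might infer that the mixed model shares the survivor-only fault. The documents do not support that. The model is exploratory, covers pain only, and can use every observed visit. It implicitly carries trajectories past death, which is a different problem, and step 5 shows no clear between-arm bias from it.

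A reader might also infer that control-arm deaths will go unrecorded. C.8.2 has the coordinator log dropout and its reasons for patients in both arms, and chart reviews are named in C.4 and C.9. These could identify deaths. What is missing is a statement that they will, with dates.

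The between-arm bias needs unequal survival. Protocol A.1 does not list longer survival among the benefits of palliative care, and eligibility includes patients with good performance status. Losses at 1 and 3 months would be smaller than at 6. All of this stands and limits the size of the point.

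Changing survey intervals is a reasonable response to mortality, because earlier surveys capture more data before death. That also stands. It is still a different decision from reducing survey burden, and a pooled percentage cannot tell the two apart.

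Finally, C.11 itself says pilots estimate effect sizes poorly, so no firm conclusion on effectiveness is at stake here.

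**Conclusion.** The point holds as a gap in labelling and reporting, with a modest possible bias. The Aim 2 score comparisons cannot be on all randomized patients as written. By default they are among patients alive and surveyed, and the 10% rule does not separate deaths from missed surveys.

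Under assumed mortality of 40–50% vs 30% and ρ of 0.3 to 0.7, the spurious difference is about 0.04 to 0.21 SD. It is smaller than the half-width of 0.51 to 0.54 SD and zero if mortality and selection are equal.

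Two stronger readings are tempting. One is that the findings on quality of life, pain and symptoms would be reversed: a shift of this size could change the sign of a small point estimate, but nothing in the documents shows that it would. The other is that mortality is certain to trigger the 10% rule: the documents give no mortality rate, and at 20% the answer turns on the denominator.

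The firmer consequences are for what the pilot hands on: precision stated for 45 complete patients per arm, and a missing-data percentage that cannot be interpreted.

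**What to change.** In the SAP:

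1. Report, by arm and visit, the numbers alive and assessed, alive and not assessed, and dead.
2. Label score comparisons as among patients alive and assessed at that visit, rather than all randomized.
3. Apply the 10% rule to missed surveys among patients alive at the visit, and report mortality separately.
4. Add one sensitivity analysis per scale on all randomized patients, with deaths ranked worst, using the Wilcoxon test already named. State how living patients without a survey enter it, and that the result mixes survival with symptoms.
5. State that date of death in both arms is taken from the planned dropout logs and chart reviews, since Table 2 lists survival only for the intervention group.

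Also reconcile the survey time points in Table 2 and C.9.1, and note that the ±1.0 to ±2.1 precision assumes a change score from all 45 patients per arm.

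The cost is SAP wording, one status table, one extra test per scale, and extracting death dates from sources already planned. The drawback is the mixed meaning of the worst-rank result, which matters where death is expected. That is why it belongs as a sensitivity analysis and not as the main comparison.

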Implementation of Home-Based Palliative Care in Limited Resource Settings

Statistical Analysis Plan

NCT04972630

June 22, 2020

Statistical Analysis Plan:

Sample Size. For this pilot study, we will recruit 45 patients in the intervention and control groups (n=90). As advocated by Leon, pilot studies "serve to check availability of eligible and willing subjects using the recruitment methods proposed, test feasibility of the treatment and measurement protocols, train researchers in study tasks, and set up data collection, checking, storage, and retrieval capabilities." Leon also noted that pilots are deficient in estimating effect size with sufficient accuracy for future study design. Thus, we will monitor the multiple process measures and obtain estimated variability of primary outcome measures. For a total sample of 90 participants, 95% CI estimates of between groups difference in change scores of palliative needs, pain, QOL and cancer symptom burden for the 2 groups can be estimated with precision ranging from ± 1.0 to ± 2.1 for standard deviations of difference scores ranging from 2.5-5.0 SD units.

Analysis Plan: Outcome measures as described in Results were collected to evaluate study aims. Data will be analyzed in SAS. All measures will be evaluated overall and by patient age, gender and cancer type and by CHW caseload. For aim 1, implementation mesures will be reported as means, standard deviations, medians, range, frequencies and proportions as appropriate. When appropriate, outcomes will be compared between intervention and control groups using t-tests and chi-square tests (or equivalent nonparametric tests) as appropriate. For primary analyses for aim 2 the intent-to-treat (ITT) sample will be used comprising all randomized patients. Descriptive statistics will be calculated for all variables. For continuous variables we will report means, standard deviation, medians and ranges. We will compare between group differences for continuous variables using either t-test for variables that are normally distributed or can be log-transformed or a Wilcoxon rank sum test for variables if normality cannot be approximated. For categorical variables, we will report frequencies, percentages and compare between group values with Chi Square or Fisher exact test. 95% CIs will be reported. In exploratory analysis to obtain variance estimates of effectiveness outcomes and the covariance structure of the longitudinal scores, generalized linear mixed models (GLMM) will be used to compare the two groups (intervention vs. control group) with intervention group as the primary independent variable and pain as the dependent variable. GLMM can account for clustering of measurements within CHW and within patients as well as accommodate missing data. Group (intervention vs. control group) will be a fixed effect; demographics (age, sex, distance from TMC cancer center); and clinical (time since diagnosis, cancer type, baseline pain) variables will be adjusted for, along with a CHW variable accounting for cluster effects among patients by CHW. We will estimate the difference (via 95% CI) in average slopes between intervention and control groups and evaluate linearity of trajectories as input to inform a future trial. Further, dropout rate will be examined. If over 10% of data are missing, we will adjust data collection intervals in a future trial.
